### **9.2.2. Additional Secondary Endpoints**

Each of the following continuous endpoints will be summarized:

- Mean change from Baseline in the Hospital Anxiety and Depression Scale (HADS) at Week 12.
- Mean change from Baseline in the Migraine Disability Assessment questionnaire (MIDAS) Test total score at Week 12.
- Mean change from Baseline in patient-rated Changes in Sexual Functioning Questionnaire Short-Form (CSFQ-14) total score in males and in females, analyzed separately, at Week 12.

For each, summary statistics (mean, SD, median, minimum, maximum) will be reported for the change from the baseline to each visit and for each of the treatment groups.

For HADS the change from baseline will be analyzed in an MMRM model with fixed effects of treatment, visit, baseline value, treatment by visit interaction, and stratification factor (preventive medication use); an unstructured covariance matrix will be used. LSMS, standard errors, and the LSM differences (each treatment vs placebo) with 95% CIs and p-values will be reported for each visit (with week 12 being of primary interest). Denominator degrees of freedom will use the Kenward Rogers approach. Should the model fail to converge, heterogeneous Toeplitz, heterogeneous first-order autoregressive, Toeplitz, first order autoregressive and compound symmetric will be attempted in that order; in these cases, the sandwich estimator (Diggle and Kenward 1994) will be used to estimate the standard errors of the fixed effects parameters and the denominator degrees of freedom will utilize the DDFM=BETWITHIN option in SAS®.

MIDAS and CSFQ are only collected at baseline and week 12, thus they will be modeled in a ANCOVA similar to the MMRM used for the repeated measures. The model will include fixed effects for treatment, baseline, and stratification factor (preventive medication use). LSMS, standard errors, and the LSM differences (each treatment vs placebo) with 95% CIs and p-values will be reported.

### **9.2.3. Exploratory Endpoints**

- Proportion of patients experiencing a  $\geq 75\%$  reduction in the number of migraine headache days from the last 28 days of Baseline to the last 28 days of treatment in each treatment group.
- Proportion of patients with fewer than 14 headache days or fewer than 8 migraine headache days per 4 weeks over the 12-week period.
- Mean change from Baseline in number of headache free days from the last 28 days of Baseline to the last 28 days of treatment.

Tonix Pharmaceuticals  
Statistical Analysis Plan: TNX-OX-CM201

A headache day is any calendar day (0:00 to 23:59) in which the patient records an attack (a headache or a migraine) in the e-diary.

For the first two exploratory endpoints, the difference in percentages in the active and placebo arms will be reported along with its 95% CI (using the Sato estimator of variance). Pairwise p-values will compare each treatment arm to placebo based on a CMH stratified by preventive medication use. Patients with missing data will be considered non-responders.

Calculation and analysis of the number of headache free days will be identical to the primary with the exception that outcome of interest will be days without headaches. Least square means (LSMs), standard errors, and the LSM differences (each treatment vs placebo) will be reported for these averages. As with the primary endpoint, Kruskal-Wallis tests will be performed and reported.

## 10. SAFETY EVALUATION

### 10.1. Overview of Safety Analysis Methods

All safety analyses will be completed for the Safety Population. All safety data will be tabulated and listed. No formal statistics or imputation will be performed for the safety analysis. The analysis of safety assessments in this study will include summaries of the following safety and tolerability data collected for each patient:

- Extent of exposure
- Incidence of Adverse Events
- Changes from baseline in clinical laboratory results
- Changes from baseline in vital signs
- Changes from baseline in electrocardiograms
- Monitoring suicidality using the Columbia Suicide Severity Rating Scale (C-SSRS)
- Changes from baseline in the HADS scores
- Changes from baseline in the CSFQ-14

### 10.2. Extent of Exposure

Duration of exposure will be calculated and summarized with descriptive statistics. The duration of exposure will be the date of last dose – date of the first dose +1, based on the first and last doses as recorded on the CRF.

Exposure days (number of days on study drug) is defined as the total number days reported in the diary that the patient took study drug. If the first dose date or last dose date from the CRF is not among the diary-reported dates, that day is added to the tally.

The duration of exposure and exposure days will be tabulated with summary statistics by treatment group. Additionally, the number of patients with duration of exposure by weeks ( $\leq 4$  weeks, 4 to  $\leq 8$ , 8 to  $\leq 12$ , and  $>12$  weeks) will be presented.

### 10.3. Adverse Events

An adverse event (AE) is defined as any untoward medical occurrence in a patient or clinical investigation patient administered an IP that does not necessarily have a causal relationship with this treatment. An AE can therefore be any unfavorable and unintended sign (including an abnormal laboratory finding, for example), symptom, or disease temporally associated with the use of a medicinal product, whether related to the medicinal product, or not.

Pre-existing diseases or conditions will not be considered AEs unless there is an increase in the frequency or severity, or a change in the quality, of the disease or condition. Worsening of a pre-existing condition is considered an AE.

Events that occur in patients treated with placebo, or during treatment free periods of the study, are also considered AEs.

An AE is defined as treatment-emergent if the first onset or worsening is during or after the first administration of IP and not more than 30 days after the last administration of study drug. In the case of missing or partial dates, an adverse event will be considered treatment-emergent unless the available data excludes that possibility.

An AE summary table will present totals for the following:

- All treatment-emergent adverse events (TEAEs)
- TEAEs by severity
- TEAEs leading to study drug discontinuation
- TEAEs by relationship (not related, unlikely related, possibly related)
- SAEs
- AEs of Special Interest (AESIs [See below])

Summaries of incidence rates (frequencies and percentages) of individual AEs by MedDRA SOC and preferred term will be prepared. Such summaries will be displayed for all TEAEs, TEAEs by maximum severity, and TEAEs by strongest relationship to study drug.

Each patient will be counted only once within each summation level (SOC; preferred term). If a patient experiences more than one TEAE within each summation level, the TEAE with the strongest relationship or the maximum severity, as appropriate, will be included in the summaries of relationship and severity.

All AEs will be presented in a listing.

These summaries will include SAEs; additionally, they will be presented separately (see below).

#### **10.4. Deaths, Serious Adverse Events, and Other Significant Adverse Events**

Summaries of incidence rates (frequencies and percentages) of individual SAEs by MedDRA SOC and preferred term will be presented. Additionally, SAEs will be listed separately.

Since intranasal administrations of agents can cause significant irritation of nasal mucosa, events of nasal irritation will be followed closely during the study and considered an AE of Special Interest (AESI); nasal cavity AEs will be identified on the CRF and additional information collected regarding the frequency, duration and temporal relationship to dosing. This information will be tabulated for the nasal cavity AEs and presented in a listing.

AESIs and TEAEs leading to discontinuation of study drug will be analyzed and presented in a manner identical to the SAEs.

Adverse events potentially related to abuse will be presented in a separate listing; terms to be used are given in Appendix 15.3. These will be compared against the current coding dictionary and any related or similar terms will be included; additional terms may be added if they are thought to potentially be related to abuse.

All deaths will be reported in a listing.

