#### **Safety Analysis**

AEs will be coded using the Medical Dictionary for Regulatory Activities (MedDRA) and will be summarized overall and by preferred term and system organ class. AEs will also be summarized by severity and relationship to study drug. Serious AEs, AEs involving the nasal passages, and AEs leading to discontinuation of study drug will also be summarized. Actual values and changes from Baseline for clinical laboratory test results, ECG parameters, vital signs, HADS scores, and CSFQ-14 scores will be summarized using descriptive statistics (n, mean, SD, median, minimum, and maximum). The number of patients with baseline and treatment-emergent suicidal ideation and/or suicidal behavior, based on the C-SSRS, will be summarized by treatment group.

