## 6.7.3 Abnormalities

Each clinically significant abnormal laboratory value or other clinically meaningful abnormality should be followed until the abnormality resolves or until a decision is made that it is not likely to resolve. If such abnormalities do not return to normal within a reasonable period, their etiology should be identified and Tonix or its designee should be notified. Clinically significant abnormalities in laboratory values after the Screening will be recorded as AEs.

NOTE: A Screening TSH level greater than 1.5 times higher than the ULN, or ALT or AST level > 2x ULN, is exclusionary; however, the patient may remain in Screening to undergo repeat liver function tests if a transient abnormality (e.g., viral illness; effects of a medication being discontinued, etc.) is thought to be responsible for their initial elevation.

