#### 7.2.8 Special Considerations

# 7.2.8.1 Adverse Events of Special Interest

Since IN administrations of agents can cause significant irritation of nasal mucosa, events of nasal irritation will be followed closely during the study and considered an AE of Special Interest. Investigators should monitor for tissue changes or lesions in the visualized nasal mucosa on nasal exam, and for pain or discomfort anywhere in the nasal cavity, sinuses or oropharynx.

Because intranasal administration of oxytocin can result in a transient, albeit short-lived and minor, rise in systemic oxytocin levels, there will be specific monitoring for the potential adverse effects of supraphysiological levels of oxytocin in plasma. It should, however, be noted that with intranasal administration and the proposed oxytocin dosing regimens, sustained and clinically relevant plasma oxytocin levels are not expected. It is out of an abundance of caution that close monitoring for potential safety signals will be carried out.

Theoretically, if substantial and sustained concentrations in plasma are achieved, plasma oxytocin may activate off target vasopressin receptors leading to antidiuretic effects. Thus, AEs that may involve changes in blood volume, blood pressure, and specific electrolyte disturbances (hyponatremia) will be AEs of special interest, e.g., new onset edema, hypervolemia, increased blood pressure, ECG changes related to cardiac hypertrophy or arrhythmia.

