# 7.2.8.4 Abuse Potential

Although no indications of abuse have been reported, oxytocin will still be monitored for abuse or misuse.

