## 10.7.3 Safety Analysis

All safety analyses will be completed for the Safety Population. All safety data will be tabulated and listed. No formal statistics will be performed for the safety analysis.

Adverse events that occur between the time written informed consent is provided and the start of study drug administration will be considered pretreatment AEs. Adverse events that start during or after study drug administration, or AEs with an onset prior to study drug administration that worsen after study drug administration will be considered TEAEs. All AEs will be coded using MedDRA, and the incidence of TEAEs will be summarized overall and by preferred term and system organ class for each treatment group. Incidence of TEAEs will also be summarized by severity and relationship to study drug. Serious AEs, TEAEs involving the nasal passages, and TEAEs leading to discontinuation of study drug will also be summarized.

Actual values and changes from Baseline for clinical laboratory test results, ECG parameters, vital signs, HADS scores, and CSFQ-14 scores will be summarized by treatment group and

visit using descriptive statistics (n, mean, SD, median, minimum, and maximum). The number of patients with baseline and treatment-emergent suicidal ideation and/or suicidal behavior, based on the C-SSRS, will be summarized by treatment group. For each laboratory test, individual patient values will be listed and values outside of the standard reference range will be flagged.

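### The protocol designates two groups of adverse events of special interest; the SAP names and identifies only the nasal one and gives no rule for selecting the second

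*SAP*

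**What the plan says.** Protocol 7.2.8.1 makes two designations. Nasal irritation is the first. The second follows from the possibility that oxytocin in plasma acts on vasopressin receptors: "AEs that may involve changes in blood volume, blood pressure, and specific electrolyte disturbances (hyponatremia) will be AEs of special interest". The examples given for it (new edema, hypervolemia, raised blood pressure, certain ECG changes) are open-ended. It is called the systemic group below.

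SAP 10.3 puts an AESI line in the AE overview table and defers the definition to later text: "AEs of Special Interest (AESIs [See below". The later text is SAP 10.4, which says: "events of nasal irritation will be followed closely during the study and considered an AE of Special Interest (AESI". It adds that nasal cavity events are identified on the CRF with extra detail. It then sets the displays: "AESIs and TEAEs leading to discontinuation of study drug will be analyzed and presented in a manner identical to the SAEs". For SAEs that means incidence by system organ class and preferred term, plus a separate listing.

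The protocol's analysis text is also narrower than its AESI section. The synopsis says: "Serious AEs, AEs involving the nasal passages, and AEs leading to discontinuation of study drug will also be summarized". Protocol 10.7.3 repeats this for treatment-emergent events: "Serious AEs, TEAEs involving the nasal passages, and TEAEs leading to discontinuation of study drug will also be summarized". Neither mentions the systemic group.

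**The concern.** The SAP plans a set of AESI displays but takes only half of the protocol's definition into the section that defines them. A programmer working from SAP 10.3 and 10.4 would have nasal events, flagged on the CRF, and nothing with which to select the systemic group.

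At stake is the AESI count by arm. The systemic group is the one the protocol ties to the drug's hypothesised systemic pharmacology, so a dose-related pattern across the two active arms and placebo is what a reader would look for there. If the displays hold nasal events alone, the AESI label in the report covers a narrower class than the one in the protocol. If someone does add the systemic group later, its open-ended definition leaves a choice of terms that could be made after unblinding.

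**Working it through.** The documents give no figure to reproduce, so the check is a comparison of texts.

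1. **Designation.** Protocol 7.2.8.1 designates 2 groups, in equally direct language. SAP 10.4 names 1 of the 2.

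2. **Identification.** For nasal events, SAP 10.4 describes a CRF flag. For the systemic group, the readable SAP gives neither a flag nor terms. Elsewhere the SAP does specify how a class is picked out:
   - Abuse-related events, which the protocol also lists among its special considerations ("Although no indications of abuse have been reported, oxytocin will still be monitored for abuse or misuse"), have a preferred-term list in SAP Appendix 15.3.
   - Migraine-specific rescue medications have a partial description in Appendix 15.5, with a final list to be documented before unblinding.

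3. **Displays that depend on the definition.** The overview row (SAP 10.3), the SAE-style table and the listing (both SAP 10.4): 1 + 1 + 1 = 3.

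4. **What other displays retain.**
   - Systemic events reported as AEs appear by preferred term in the TEAE tables, and in the listing of all AEs (SAP 10.3).
   - Laboratory findings can become AEs: "Clinically significant abnormalities in laboratory values after the Screening will be recorded as AEs" (Protocol 6.7.3).
   - SAP 10.5 gives shift tables for each analyte at each scheduled time point and flags out-of-range values. Sodium is in the chemistry panel (Protocol 6.7.1), so it is covered.
   - SAP 10.6.1 gives blood pressure and weight changes with 95% confidence intervals.
   - SAP 10.6.2 gives changes in ECG parameters and counts by interpretation category.

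5. **What they do not retain.** SAP 10.3 counts each patient once within a preferred term and once within a system organ class. A patient with both edema and hyponatremia is counted under each term, so the rows cannot be added to give the number of patients per arm with any systemic event. The displays in SAP 10.5 and 10.6 summarise measurements, not reported events, and name no parameter for edema or hypervolemia. The grouped patient count is therefore the one thing that the AESI displays alone would supply.

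**The case against.** The best reply has four parts.

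- **The SAP does not say that nasal events are the only AESIs.** It uses the plural, calls nasal irritation one such event, and in SAP 2 encourages the reader to consult the protocol. Analysts could read the term in the protocol's sense. This stands: omission is likely from the SAP text, not certain. That reading still leaves no selection rule, because the protocol's definition is broad and its examples are open.

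- **SAP 13, on changes from the protocol, is redacted.** A deliberate narrowing may be declared there. The CRF is also not available, so a flag for other AESIs cannot be excluded. This stands as a limit on the point.

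- **SAP 10.4 delivers every separate AE summary that the protocol's analysis sections promise.** Those are serious events, nasal events, and events leading to discontinuation of study drug. Protocol 7.2.8.1 prescribes no table, describes the monitoring as precautionary, and does not expect sustained, clinically relevant plasma levels. This is correct, and it puts part of the inconsistency inside the protocol. It lowers the weight of the point but does not withdraw the designation.

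- **Much of the underlying information is displayed elsewhere**, and no formal safety testing is planned. This also stands, and it is why the point is minor.

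A reader might go further and infer that the SAP has removed the systemic group from safety reporting, or that hyponatremia and blood pressure findings would go unseen. The documents do not support either. The SAP nowhere excludes the group, and the events and measurements remain in the displays listed under the check.

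**Conclusion.** This is a protocol-SAP inconsistency of minor severity. The protocol designates two AESI groups. The readable SAP names one and gives no rule for selecting the other. Built from the SAP text, the three AESI displays would cover a narrower class than the protocol designates.

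That conclusion assumes that the redacted text does not supply or explain the difference, and that the analysts do not bring in the second group from the protocol themselves. If either assumption fails, what remains is that SAP 10.4 as readable does not show how the second group is identified.

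The consequence is confined to grouped AESI counts by arm. No collected data and no efficacy result are affected.

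**What to change.** Reconcile Protocol 7.2.8.1 with the synopsis safety analysis, Protocol 10.7.3, and SAP 10.3 and 10.4.

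- Name the second AESI group in SAP 10.4.
- Identify it with a preferred-term list documented before unblinding. Appendix 15.5 sets that timing for rescue medications. Appendix 15.3 is a model for the format only, since SAP 10.4 leaves it open to added terms and ties it to no date.
- Show the second group by arm, separately from nasal events, in the overview row, the table and the listing.
- If the narrowing to nasal events is intended, say so in the SAP and give the reason.

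The cost is SAP wording, one term list and extra rows in displays already planned. It needs no new data collection and no formal safety test.

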## 15.3. AEs Potentially Related to Abuse

The following preferred terms will be used to identify AEs potentially related to abuse.

- Euphoric mood
- Elevated mood
- Feeling abnormal
- Feeling drunk
- Feeling of relaxation
- Dizziness
- Thinking abnormal
- Hallucination
- Inappropriate affect
- Psychosis
- Aggression
- Confusion
- Disorientation
- Drug tolerance

[figure not shown]
Tonix Pharmaceuticals  
Statistical Analysis Plan: TNX-OX-CM201

- Habituation
- Drug withdrawal syndrome

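### SAP 10.4 carries over only nasal irritation as an AESI, so on the visible text the AESI total and tables would leave out the protocol's blood-volume, blood-pressure, hyponatremia and ECG-change group

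*SAP*

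**What the plan says.** Protocol 7.2.8.1 first makes nasal irritation an AESI. It then gives a mechanism for a second group (off-target vasopressin-receptor activation with antidiuretic effects) and states that "AEs that may involve changes in blood volume, blood pressure, and specific electrolyte disturbances (hyponatremia) will be AEs of special interest". Its examples are "new onset edema, hypervolemia, increased blood pressure, ECG changes related to cardiac hypertrophy or arrhythmia".

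SAP 10.3 lists the lines of the adverse event summary table. One is "AEs of Special Interest (AESIs [See below", so the definition is left to later text. SAP 10.4 is the only later text that supplies one: "events of nasal irritation will be followed closely during the study and considered an AE of Special Interest (AESI". It adds that "nasal cavity AEs will be identified on the CRF and additional information collected regarding the frequency, duration and temporal relationship to dosing". It also sets the outputs: "AESIs and TEAEs leading to discontinuation of study drug will be analyzed and presented in a manner identical to the SAEs". For SAEs that means incidence by system organ class (SOC) and preferred term, plus a separate listing.

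The SAP names the second group as AESIs nowhere and gives no term list for it. Appendix 15.3 does give such a list for another purpose: "The following preferred terms will be used to identify AEs potentially related to abuse".

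Protocol 10.7.3 and the synopsis plan separate adverse event summaries for serious events, nasal-passage events and events leading to discontinuation. Neither mentions a separate summary of the second AESI group.

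**The concern.** A table line headed AESI will be read against the protocol's definition. If it is built from SAP 10.4 as it stands, it will look complete while containing nasal events only. The events left out are the ones the protocol singled out as possible signs of systemic oxytocin exposure.

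The information lost is narrow. The component events remain in the general tables of treatment-emergent adverse events (TEAEs), but no planned output gives the number of patients per arm with at least one event in the group. Adding table rows does not recover that number, because "Each patient will be counted only once within each summation level (SOC; preferred term". A patient with both edema and raised blood pressure counts in two rows.

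**Working it through.** There is no figure in the plan to reproduce. The main check is a comparison of texts.

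**Where each AESI group is carried through**

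| Item | Nasal irritation | Blood volume, blood pressure, hyponatremia, ECG changes |
|---|---|---|
| Designated an AESI, protocol 7.2.8.1 | yes | yes |
| Separate summary planned, protocol 10.7.3 | yes | no |
| Named as an AESI, SAP 10.4 | yes | no |
| Means of identification given in the SAP | CRF flag (10.4) | none |
| In the AESI total (10.3) and AESI tables (10.4), as visible | yes | no |
| In general TEAE tables and the all-AE listing (10.3) | yes | yes |
| Related measurements summarised by arm | not checked here | sodium (10.5), blood pressure (10.6.1), ECG (10.6.2) |

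The protocol has two groups and the SAP carries over one.

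**Why rows cannot be added.** Assume 6 affected patients in an arm of 100 (the arm size is from the protocol's study schema; 6% is an assumption). If 30% of them have a second event type, the rows sum to 6 × 1.3 = 7.8 for 6 patients.

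**What a group row could show, and how noisy it would be.** Let X be the number of affected patients in an arm, binomial with n = 100. For one active arm against placebo,

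P(excess ≥ 3) = Σ_y P(X_plc = y) · P(X_act ≥ y + 3).

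For either of two active arms,

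P = Σ_y P(X_plc = y) · [1 − (1 − P(X_act ≥ y + 3))²].

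With no drug effect (all risks are assumptions):

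| Risk in every arm | Either active arm 3 or more above placebo |
|---|---|
| 1% | 7% |
| 2% | 18% |
| 3% | 25% (14% for one named arm) |
| 5% | 33% |

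With an assumed drug effect in one active arm, the table below gives the chance of an excess of 3 or more patients, first in the group row and then in at least one of six component rows. Six is a count of the protocol's examples plus hyponatremia, taking the ECG phrase as two types. The protocol's list is illustrative, so six is itself an assumption. Component rows were simulated with one event type per affected patient.

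| Active vs placebo | Group row | Some single row, even split | Some single row, one type is 70% of events |
|---|---|---|---|
| 4% vs 1% | 0.58 | 0.15 | 0.40 |
| 6% vs 2% | 0.70 | 0.32 | 0.55 |
| 10% vs 3% | 0.91 | 0.68 | 0.82 |

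The group row shows the excess more often than any single row does. The gain depends heavily on how events divide among types: at 6% vs 2% the single-row figure runs from 0.32 to 0.55, against 0.70 for the group.

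**The case against.** The strongest reply is that the SAP follows the protocol's own analysis section. Protocol 10.7.3 and the synopsis ask for a separate summary of nasal events only. Section 7.2.8.1 presents the systemic monitoring as precautionary, expects no sustained and clinically relevant plasma levels, and promises no AESI table. This stands, and it places the start of the mismatch inside the protocol. It does not settle the matter, because SAP 10.3 and 10.4 do promise AESI outputs and protocol 7.2.8.1 is the only place where the protocol says what AESIs are.

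Second, SAP 10.4 calls nasal irritation an AESI, not the only one, and SAP section 2 encourages the reader to consult the protocol. A programmer could apply the protocol's wider definition. A reader might infer that the SAP excludes the second group; the text does not say so. The supportable claim is that the SAP does not carry the group over or make it operational. SAP 13, the list of changes from the protocol, is blacked out and could contain a declared narrowing. The CRF is not among the documents, so a flag for the second group may exist there.

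Third, a reader might infer that these events would disappear from the report. They would not. TEAEs are tabulated by SOC and preferred term, severity and relationship, and all AEs are listed. Every analyte, including sodium, gets a shift table and change from baseline with a 95% CI. Blood pressure gets change with a 95% CI, and ECG interpretations get n (%) by category. A grouped count could be derived from the listing once someone had settled which terms belong.

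Fourth, a reader might infer that those terms would be chosen after unblinding. Nothing in the documents says when or how they would be chosen. Nor does the point extend to counting patients who cross blood-pressure cut-offs: protocol 10.7.3 asks for descriptive statistics on vital signs, and SAP 10.6.1 provides them.

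**Conclusion.** The concern holds as a minor inconsistency. On the visible text, the AESI total and tables would cover one of the protocol's two AESI groups, and the number of patients per arm with any blood-volume, blood-pressure, hyponatremia or ECG-change event would not be stated. The conclusion rests on the text comparison. It assumes that the redacted SAP 13 and the unseen CRF do not already resolve the matter.

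The simulated figures only illustrate what a grouped count adds. They rest on assumed event rates and on how events split among types, and they do not show that a real signal would be missed. The primary efficacy conclusion is unaffected.

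**What to change.** In SAP 10.4, name the protocol's second group as AESIs beside nasal irritation: blood-volume/edema, blood-pressure, hyponatremia and ECG-change events. Fix the preferred terms before unblinding in a short appendix like 15.3. Give the group its own by-arm n (%) row in the summary table, counting each patient once, and include it in the AESI tables and listing already promised. Keep it descriptive, in line with the rule against formal safety statistics in protocol 10.7.3 and SAP 10.1.

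If the narrowing was intended, say so with the reason, and bring protocol 7.2.8.1, protocol 10.7.3 and SAP 10.4 into agreement.

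The cost is a sentence, a term list and a few tables from data already collected. The downside is small counts that chance can move, so the row should not be read as a test.
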